### **3.1 Inclusion Criteria**

Eligible participants will include women who:

- 3.1.1 Participants in the Childhood Cancer Survivor Study (CCSS);
- 3.1.2 Were diagnosed with a childhood cancer prior to the age of 21 years;
- 3.1.3 Were treated with  $\geq 10$  Gy of chest RT (recent revision with a lower dose threshold);
- 3.1.4 Do not have a history of breast cancer;
- 3.1.5 Have not had both a breast MRI *and* mammogram in the previous 24 months;
- 3.1.6 Do not have a contraindication to MRI (i.e., pacemaker);
- 3.1.7 Are 25 years of age or older at time of enrollment;

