To explore moderating factors that may be associated with obtaining a breast MRI and a mammogram, we will use mixed effects models. The mixed model is  $\mathbf{Y}_i = \mu(\mathbf{X}_i, \alpha, \mathbf{Z}_i, \mathbf{b}_i) + \mathbf{e}_i$  where for participant  $i$ ,  $\mathbf{Y}_i$  is the response vector capturing whether the participant had a breast MRI and mammogram,  $\mathbf{X}_i$  is a fixed effects design matrix that includes indicators for treatment group, randomization strata, assessment time (baseline and end-of-study), potential confounders, and moderator variables,  $\mathbf{Z}_i$  is a design matrix for the random effects that would allow random subject deviations from the population average response,  $\alpha$  contains the fixed effects regression coefficients,  $\mathbf{b}_i$  contains the random effects coefficients,  $\mathbf{e}_i$  is the vector of error terms, and  $\mathbf{b}_i$  and  $\mathbf{e}_i$  are normally distributed with means of zero. We will test whether variables significantly moderate having a breast MRI or mammogram by testing whether the regression coefficients associated with these variables are significantly different from zero. Further, by including interaction terms between potential moderating variables and the treatment group indicator, we will test whether the effectiveness of the intervention differs by the moderating factors.

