### 6.2 Sample Size and Power

The primary aim involves two pair-wise comparisons of equal importance. For each comparison, we fix the probability of a Type I error at 0.025 in order to maintain the overall probability of a Type I error at 0.05. We powered the study to detect a difference of 20% for each pair-wise comparison assuming equal randomization to each of the three arms and that the proportion of women in the control group who will have a mammogram and an MRI will be approximately 10% based on our previous work. Table 1 shows the power we expect to have using two-sided Mantel-Haenszel tests and indicates that we should have sufficient power to detect a clinically meaningful difference even if the proportion of women in the control arm with the primary endpoint is somewhat higher than we expect. The power calculation of the Cochran-Mantel-Haenszel tests assumes a common risk ratio among the strata, that all strata generate the same proportion for the control arm and intervention arm.

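### The moderator model puts a normal error on a yes/no outcome; fitted with constant variance, its interaction tests can be too liberal or too conservative

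*Combined protocol and SAP*

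**What the plan says.** Section 6.0 (Statistical Analyses) writes the moderator model as a mean function of fixed and random effects plus an additive error. The response "is the response vector capturing whether the participant had a breast MRI and mammogram". The random-effects part "is a design matrix for the random effects that would allow random subject deviations from the population average response". The fixed effects include treatment group, randomization strata, "assessment time (baseline and end-of-study), potential confounders, and moderator variables". The only distributional statement is that the random effects and errors "are normally distributed with means of zero".

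The model is used for testing. Coefficients of the candidate factors are compared with zero, and differences in effectiveness are tested "by including interaction terms between potential moderating variables and the treatment group indicator". The section gives no link function, binomial distribution, variance or covariance structure, robust standard error or interaction scale. The purpose is exploratory: "To explore moderating factors that may be associated with obtaining a breast MRI and a mammogram". It serves objective 2.1.3. The primary and secondary comparisons use the Cochran-Mantel-Haenszel test instead.

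**The concern.** Once its mean is subtracted, a yes/no response takes only two values, so its error cannot be normal whatever shape the mean function has. Its variance is also tied to its mean: p(1 − p) is 0.09 at 10%, 0.21 at 30% and 0.25 at 50%. A normal-error model fitted in the usual way pools these into one residual variance. If a small moderator group has higher screening rates than the rest, the pooled variance is too small for the cells that dominate the interaction, and the test rejects too often. If the small group has lower rates, the test hardly ever rejects.

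At stake is which patient and provider factors are reported as changing the effect of the interventions. Two analysts following the same paragraph could reach different answers.

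**Working it through.** **The plan's own figure.** None is given for this analysis. Table 1 in section 6.2 concerns the primary comparison, where "we fix the probability of a Type I error at 0.025". Its 10% versus 30% row (90% power) is reproduced by a standard two-proportion calculation: 90.0% with 97 per arm and no continuity correction, or 90.1% with 107 per arm and a correction. That does not bear on the moderator model.

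**Inputs from the documents.** 320 women randomized 1:1:1 (sections 3.0 and 3.2) give 320/3 ≈ 107 per arm. Planning rates are about 10% in control and 20 points more with intervention (section 6.2). For group sizes, section 3.2 offers an 18% minority enrolment goal (0.18 × 107 ≈ 19 per arm, leaving 88) and 8% without a primary care provider in EMPOWER-I (0.08 × 107 ≈ 9, leaving 98). These shares are used only as plausible sizes.

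**Assumed inputs.** The documents give no screening rates by moderator group, so all such rates below are assumptions. Every setting has zero interaction on the risk-difference scale.

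**Formulas.** One intervention arm against control gives four cells with sizes n and rates p.
- True SE of the interaction = √[Σ p(1 − p)/n]
- Constant-variance SE = √[s² · Σ 1/n], where s² = Σ n·p(1 − p) / Σ n

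**Setting A in full** (small group 35% vs 55%, rest 5% vs 25%):
- True variance = (0.2275 + 0.2475)/19 + (0.0475 + 0.1875)/88 = 0.0250 + 0.0027 = 0.0277; SE 0.166.
- s² = (19 × 0.475 + 88 × 0.235)/214 = 0.1388; Σ 1/n = 2/19 + 2/88 = 0.1280; model SE = √(0.1388 × 0.1280) = 0.133.
- True/model = 0.166/0.133 = 1.25. The nominal 5% cut-off of 1.96 acts like 1.96/1.25 ≈ 1.57, a two-sided error of about 12%.

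The same steps for the other settings, with rejection rates from 40,000 simulated trials each (pooled residual variance):

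| Setting | Small group, n per arm and rates | Rest, n per arm and rates | True SE | Model SE | True/model | Rejection at nominal 5% |
|---|---|---|---|---|---|---|
| A | 19; 35% vs 55% | 88; 5% vs 25% | 0.166 | 0.133 | 1.25 | 11.7% |
| B | 19; 25% vs 45% | 88; 7% vs 27% | 0.161 | 0.137 | 1.17 | 9.7% |
| C | 19; 3% vs 13% | 88; 20% vs 30% | 0.108 | 0.145 | 0.74 | 0.8% |
| D | 9; 2% vs 12% | 98; 11% vs 21% | 0.129 | 0.175 | 0.74 | 1.0% |
| Modest gap | 19; 15% vs 35% | 88; 9% vs 29% | 0.148 | 0.139 | 1.07 | 6.9% |
| Equal rates | 19; 10% vs 30% | 88; 10% vs 30% | 0.139 | 0.139 | 1.00 | 5.0% |
| Even split | 53; 25% vs 45% | 54; 5% vs 25% | 0.112 | 0.112 | 1.00 | 4.8% |

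Settings A and B average to the planning rates: for A, (19 × 0.35 + 88 × 0.05)/107 = 10.3% in control and (19 × 0.55 + 88 × 0.25)/107 = 30.3% with intervention.

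**Does the random effect remove the problem?** A small mixed-model run with two time points (150 trials, baseline response set to 0, a 20% group at 25% vs 45% and the rest at 5% vs 25%) gave a model SE of 0.128 against an empirical 0.151. The mixed-model runs gave frequent boundary warnings, so this is only supporting evidence.

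**Do the obvious replacements work?**
- Heteroscedasticity-robust SEs reject 5.4%, 5.6% and 5.6% in A, B and C, but about 15% in D.
- Logistic regression tests a different null. In A the odds ratios are (0.55/0.45)/(0.35/0.65) = 2.27 and (0.25/0.75)/(0.05/0.95) = 6.33, and a Wald interaction test rejects about 20%, which is a real interaction on that scale.
- Empty cells are common in sparse groups. In C the chance of at least one is 1 − (1 − 0.97¹⁹)(1 − 0.87¹⁹) ≈ 59%; in D it is 1 − (1 − 0.98⁹)(1 − 0.88⁹) ≈ 89%. Counting those trials as non-rejections, the logistic Wald test rejects below 0.1% in both.

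**The case against.** The strongest reply is that a reader might infer that the plan fixes one common variance and that its standard errors are therefore wrong. The documents support neither step. Section 6.0 states normality and mean zero only, and its mean function is general enough to be nonlinear. Distortion needs three things together: constant variance, unequal groups and different rates. Without the second or third, the test holds its level. This stands, and the point is worded to match.

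The larger figures also rest on wide assumed gaps: setting A puts 30 points between moderator groups, and a modest gap gives only 6.9%. The one 18% group the protocol names is the minority enrolment goal, and for race/ethnicity sections 3.2 and 6.0 report or expect no difference. Many listed moderators in section 5.2 are scales, not small dichotomies. This stands as a limit on size. Wide gaps are not implausible in this population, however: section 1.0 reports mammography of 76.0% versus 17.6% by physician recommendation at ages 25–39.

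The calculation is simpler than the plan's model, which has three arms, two time points, strata and confounders. That also stands.

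What does not stand is that this is merely missing detail. An additive normal error is stated, and it cannot hold for a yes/no response under any mean function.

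**Conclusion.** The point holds in a limited form. The stated error distribution is wrong for the outcome, and nothing else in the section protects the interaction tests. If constant variance is used, the true standard error was between 0.74 and 1.25 times the model's in the unequal-group settings tabulated, with rejection from 0.8% to 11.7% at a nominal 5%. There was no material error with an even split or equal rates. These sizes depend on assumed group rates and on the inferred constant variance.

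A reader might also infer that the trial's main conclusions are at risk. They are not. The primary and secondary comparisons use Cochran-Mantel-Haenszel tests and do not pass through this model. Only exploratory objective 2.1.3 is affected. Correction is still worthwhile because the model is used to declare moderators and the change is cheap.

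**What to change.** In section 6.0, replace the normal-error mixed model for moderators with a binary-outcome analysis of the end-of-study response, with arm, strata, moderator and arm-by-moderator terms. Baseline characteristics can enter as covariates. Dropping the baseline response loses little: eligibility criterion 3.1.5 ("Have not had both a breast MRI *and* mammogram in the previous 24 months") makes it zero for essentially everyone, which does not fit a single error variance across times and could cause separation in a two-time logistic model.

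State the interaction scale in advance:
- For risk differences, the scale of the primary estimate, use a linear model with heteroscedasticity-robust standard errors.
- For odds ratios, use logistic regression, and note that no interaction on one scale is generally an interaction on the other.
- For sparse moderator groups (for example about 9 women per arm, or any empty or full cell), use an exact or penalised-likelihood method, or report descriptively.

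The cost is analysis-plan wording only. No new data and no design change are needed.

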## EMPOWER-II

To explore mediating factors, we will follow MacKinnon and colleagues' recommendations and examine potential factors in a post-hoc manner and make necessary adjustments. For example, we will fit path analysis models using the statistical packages LISREL or EQS, inspect the path coefficients, and choose the appropriate statistical tests of mediating effects according to MacKinnon et al. We may also consider testing model equivalence to examine whether the mediating path model is equivalent across the control and intervention groups. While several different tests have been used to test mediating factors, MacKinnon and colleagues recommend using tests developed from the product of coefficients methods, where the parameters are estimated using regression, and the standard error of their product is obtained by the delta method. This test can be readily implemented using software made available by MacKinnon et al. All analyses will be adjusted for the stratification factors used at randomization.

Costs for each component of the intervention will be collected to determine the cost per person. This will include the dollar costs of the materials, personnel time for creating the cancer treatment summaries, PopSockets, mailings, and notifications/app messaging/mobile data costs. From this data, we will estimate a dollar cost and time cost per person. This will not include the costs for developing the materials, as our goal is to determine the dissemination cost per person. Upon completion of the study, we will have developed several "deliverables" that can be disseminated for use by other investigators. These will include the cancer treatment summary template, harms and benefits of cancer surveillance information, and patient and physician education handouts. These materials will be made publicly available on the CCSS website: <http://www.stjude.org/ccss>.

We will identify utilization of screening and diagnostic imaging (breast MRI, mammography, and ultrasound), diagnostic procedures (fine needle aspiration, core needle biopsy and excisional biopsy), breast surgery, and non-procedure breast-related physician visits. Each service will be multiplied by a unit cost amount in order to estimate total costs. We will use Medicare's 2008 Direct Practice Expense and Resource Based Relative Value Scale (RBRVS) to estimate average unit costs for physician and laboratory services. Although most study participants will not be Medicare beneficiaries, Medicare's reimbursement methodology was developed to reflect true resource costs. For this reason, Medicare reimbursement may be used as a proxy for unit cost, even when the population of interest is not limited to Medicare beneficiaries. This costing methodology has been employed in economic analyses related to screening mammography. In sensitivity analysis, we will evaluate a range of unit cost estimates, both lower and higher than the average Medicare reimbursement level. Patient time and travel costs will be estimated from the literature.

Our assessment of the downstream costs of the intervention, as well as the cost of the intervention itself, will allow us to perform a limited cost-effectiveness analysis. Specifically, we will estimate the cost per additional patient screened and the cost per additional breast cancer case detected as a result of the intervention. Because these health outcomes do not capture events that follow breast cancer diagnosis, our cost estimates will not include the costs of events that follow diagnosis (e.g., costs of breast cancer treatment). As previously mentioned, we will not conduct formal hypothesis tests on the economic outcomes given the primary focus of the trial on non-economic endpoints (and sample size requirements associated with these endpoints). Resource utilization and cost data are typically skewed, and therefore the sample size of the trial will likely be insufficient to detect significant differences in costs between study arms. The economic impact of the intervention will be evaluated using standard incremental cost-effectiveness analysis methods, and sensitivity analysis will be used to assess the impact of assumptions and uncertainty on results and conclusions. This analytic approach is appropriate in economic studies that "piggyback" randomized trials.

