## 3.0 Participant Recruitment and Enrollment

We will enroll 320 women from the Childhood Cancer Survivor Study (CCSS), alternatively known as the Long-Term Follow-Up Study (LTFU) to participants. The CCSS is a multi-institutional, multi-disciplinary collaborative research resource established to systematically evaluate long-term outcomes among children

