## EMPOWER-II

diagnosed with cancer who survived five or more years from diagnosis. Participants will be recruited in three waves (97/wave) by the CCSS Coordinating Center, which has extensive experience recruiting for our studies. We anticipate enrolling 97 participants in Year 1 and then the remaining 194 in Year 2. All eligible members of the CCSS cohort will be identified by the CCSS Statistical Center. We will randomly sample CCSS members from this eligibility list to contact regarding participation in this study.

An introductory letter of invitation will be sent via e-mail by the CCSS Coordinating Center. Included in this e-mail will be (1) an invitation to join the EMPOWER-II study; (2) instructions on how to download the Eureka platform and (3) a brief summary of study activities. A second letter will be sent to non-responders via regular mail. After 3 weeks, a telephone interviewer from the CCSS Coordinating Center will then call potentially eligible cohort members who fail to respond to 2 invitation letters and invite them to participate. After 3 weeks, a final invitation letter will be sent via regular mail. Once interested participants have downloaded the Eureka app, they will receive push notifications leading them to an FAQ sheet and eligibility checklist within the app. Eligible participants will then receive an electronic consent form via the app along with a HIPAA waiver, and a link to the privacy policy of Eureka. We will continue attempting to accrue subjects from the eligibility list until 320 members have been randomized in the study. With over 1,400 women in the CCSS potentially eligible for this study and the high participation rate in EMPOWER-I, we do not anticipate a problem in enrolling 320 participants. During the study enrollment, there will be an estimated 1,456 women who fulfill the eligibility criteria.

All participating survivors will be compensated \$50 for each survey completed at baseline and at the end of the study (\$100 total for each survivor). We will also compensate PCPs for their time in answering the short survey at baseline and at the end of the study. We will compensate at the same rate as the survivor participants: \$50 per survey (\$100 total for each PCP).

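### The only mediation test the plan describes is conservative if read in the usual way, and it should be replaced by a named interval or joint-significance test before the path coefficients are seen (exploratory analysis only)

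*Combined protocol and SAP*

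**What the plan says.** Objective 2.1.3 is to explore mediating and moderating factors. The mediation paragraph of section 6.0 says the investigators will "examine potential factors in a post-hoc manner and make necessary adjustments". As an example, "we will fit path analysis models using the statistical packages LISREL or EQS", after which they will "inspect the path coefficients, and choose the appropriate statistical tests of mediating effects". It then reports that the cited methods authors "recommend using tests developed from the product of coefficients methods", with parameters estimated by regression, and that "the standard error of their product is obtained by the delta method". It adds that this test is easy to run with those authors' software. Adjustment for the randomisation strata is promised.

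The paragraph does not give a reference distribution or critical value, a significance level for mediation, or a model for a binary outcome in the path analysis. It names no bootstrap, product-distribution or joint-significance procedure. The endpoint is yes/no: the moderator model in the same section describes "the response vector capturing whether the participant had a breast MRI and mammogram", and the primary outcome is the same variable.

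**The concern.** A delta-method standard error is normally used by dividing the estimated product by it and comparing the ratio with a standard normal. The product of two normal estimates is not itself normal unless at least one path is many standard errors from zero. In the usual use the test therefore rejects too rarely. Patient activation, self-efficacy, knowledge, barriers and affect are measured largely to learn how the interventions work. A needlessly conservative test could report no mediation for a component that was active, when another analysis of the same data would have found it.

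**Working it through.** **The plan's own figure.** There is none. The documents give no power, effect size or significance level for mediation; Table 1 in section 6.2 concerns the primary comparison only.

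**Inputs from the documents.** 320 women randomised 1:1:1, so 320/3 = 106.7, taken as 107 per arm. (The recruitment text also implies 3 × 97 = 291, or 97 per arm.) Control rate 10%. Binary outcome.

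**Assumptions.** Path a is the arm effect on the mediator in SD. Path b is the log odds ratio for the outcome per SD of mediator. Two-sided 5%, one intervention arm against control, no strata, no missing data.

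**Step 1: why the ratio is conservative.** With Za = a/SE(a) and Zb = b/SE(b),

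ab / √(a²·SE(b)² + b²·SE(a)²) = Za·Zb / √(Za² + Zb²).

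If both paths have Z = 2.5, each is significant alone, but the ratio is 2.5/√2 = 1.77, below 1.96. With equal Z values, each must exceed 1.96 × √2 = 2.77. This needs no binary outcome and no particular sample size.

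**Step 2: where this trial sits.** The expected Z for path a is a/√(2/107): 2.2 at 0.3 SD, 2.9 at 0.4, 3.7 at 0.5. At 97 per arm the same shifts give 2.1, 2.8 and 3.5. A large-sample calculation (400,000 draws) gives the power of the delta-method test as a fraction of joint-significance power:

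| Expected Z, path a / path b | Ratio |
|---|---|
| 2.0 / 2.0 | 0.35 |
| 2.5 / 2.5 | 0.52 |
| 2.8 / 2.8 | 0.64 |
| 3.24 / 3.24 | 0.79 |
| 4 / 4 | 0.95 |
| 2.8 / 5 | 0.92 |

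**Step 3: simulation at 107 per arm** (3,000 replicates, logistic outcome, control rate 10%, intervention rate about 25% to 28%, simulation standard error at most 0.9 points):

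| a (SD) | b (log OR) | Delta method, normal | Joint significance | Monte Carlo interval |
|---|---|---|---|---|
| 0.4 | 0 | 0.7% | 3.5% | 3.2% |
| 0 | 0.6 | 1.4% | 4.3% | 3.8% |
| 0.3 | 0.4 | 13% | 35% | 31% |
| 0.4 | 0.4 | 25% | 48% | 45% |
| 0.4 | 0.6 | 51% | 74% | 72% |
| 0.5 | 0.6 | 68% | 84% | 83% |
| 0.5 | 0.8 | 87% | 94% | 94% |
| 0.8 | 0.8 | 97% | 98% | 98% |

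The first two rows are type I error. When both paths are null, every method is far below nominal: 0.0% to 0.1% for the delta method and 0.2% to 0.3% for the others.

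**Step 4: repeatability.** Two further simulations of the same comparison gave, for delta method against Monte Carlo interval:
- 0.3/0.4: 11% against 27%, and 12% against 28%.
- 0.35/0.5: 27% against 51%, and 31% against 57%.
- 0.5/0.6: 68% against 82%, and 72% against 86%.
- Type I error: 0% to 0.8% for the delta method.

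**Step 5: other choices the plan leaves open.** Pooling both intervention arms against control (213 against 107) gives 31% against 53% at 0.3/0.4, about 60% against 75% to 78% at 0.35/0.5, and 94% against 97% to 98% at 0.5/0.6. At a significance level of 0.025, as used for the primary comparisons, the ratio to joint significance at 0.3/0.4 falls from 0.37 to 0.22.

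**The case against.** The strongest reply is that the plan does not commit to this test. The path models are given as an example, the test is to be chosen later, and the delta-method sentence reports what a cited paper recommends. That stands: a reader might infer that the test is fixed, and the text does not say so. But it is the only test described, no rule for choosing another is given, and a choice made after seeing coefficients is itself a reason to name one beforehand.

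The normal reference is also an inference. The plan names none and defers to software that cannot be examined here. It mentions no mediation confidence interval either, so the documents do not support saying that its intervals are wrong.

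Three further readings are tempting and do not hold:
- That power is roughly halved in general. The relative loss against joint significance runs from about 63% to about 1% across the assumed effects, and the documents supply none of those effects.
- That the binary outcome or the arm size causes the conservatism. Step 1 shows the cause is the product's distribution; outcome type and sample size act only through how precisely each path is estimated.
- That most real mediators of moderate size would be missed. At 0.5/0.6 the delta-method test still detects about 68%, and at 0.3/0.4 the replacement also misses most.

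Finally, the analysis is exploratory, section 5.2 lists about ten candidate factors with no multiplicity control, and a conservative screen does not inflate false positives. That limits the consequence. It is not a reason to keep the test: its true level varies with the unknown paths, so it is not a controlled form of caution. If a stricter level is wanted, it can be stated.

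**Conclusion.** The point holds in a limited form, as an optional improvement. If the described ratio is referred to the normal distribution, type I error is about 1% at nominal 5% when one path is null. At 107 per arm the power loss against a Monte Carlo interval is half or more when both paths are weak (about 12% against 28% at 0.3/0.4), about 14 points at 0.5/0.6, and negligible when both are strong. It is smaller if the intervention arms are pooled. These sizes rest on assumed path effects, a 5% level, the normal reference, and simulations without strata or missing data. Only objective 2.1.3 is touched; the primary comparisons and their conclusions are unaffected.

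**What to change.** In the mediation paragraph of section 6.0, replace the delta-method test with a percentile-bootstrap interval or a Monte Carlo product-distribution interval for the indirect effect, or with the joint-significance test. Specify a regression model for each mediator and a logistic model for the yes/no outcome, both with the strata adjustment already planned. State the significance level and whether the contrast is each intervention arm against control or the two pooled. Fix all of this before the path coefficients are seen, in place of choosing the test after inspecting them.

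The cost is a few sentences of analysis plan and standard software. No new data, sample size change or change to the primary analysis is needed. The change will not remove the conservatism shared by all these methods when both paths are null.

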### COVID-19 Response

Study outcomes may be affected by the loss of jobs and/or health insurance of study participants due to the COVID-19 pandemic. In light of this, the study period for participants who consented or who received a study invitation prior to the COVID recruitment hold will be extended to 18 months. These participants will receive their end-of-study survey through the Eureka app once they complete their screening tests (mammogram and/or breast MRI) or at approximately 18 months, whichever is sooner. An email from the Principal Investigator will be sent to current participants informing them of this change.

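### Downstream services are priced from Medicare's 2008 schedule, about 9 to 12 or more years before they occurred, with no common price year for the costs that are combined

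*Combined protocol and SAP*

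**What the plan says.** The economic part of Section 6.0 (Statistical Analyses) builds downstream cost from service counts: "Each service will be multiplied by a unit cost amount in order to estimate total costs". The source of those unit costs, for physician and laboratory services, is fixed: "We will use Medicare's 2008 Direct Practice Expense and Resource Based Relative Value Scale (RBRVS". Patient time and travel costs are to come from the literature, with no price year given. A sensitivity analysis is to vary unit costs above and below the average Medicare level; neither its width nor its year is stated.

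The programme's own costs are handled separately: "Costs for each component of the intervention will be collected to determine the cost per person". They cover materials, personnel time, PopSockets, mailings and messaging.

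The two parts then meet. The downstream costs, "as well as the cost of the intervention itself, will allow us to perform a limited cost-effectiveness analysis", and the outputs are named: "we will estimate the cost per additional patient screened and the cost per additional breast cancer case detected as a result of the intervention".

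On timing, Section 4.0 (COVID-19 Response) says that the study period for participants who consented or were invited "prior to the COVID recruitment hold will be extended to 18 months".

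**The concern.** The year 2008 is the only price year in the economic plan, and the trial took place long after it. An analyst who follows the text would value imaging, biopsies, surgery and breast-related visits on the 2008 schedule. The analyst would then add programme costs recorded around a decade later, and time and travel costs from whatever year the literature source used. The total would be in no single year's dollars.

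The costs resulting from the interventions (the second part of Objective 2.1.4), the cost per additional woman screened and the cost per additional cancer detected all use this total. Section 2.2 rules out hypothesis tests on economic outcomes, so the estimates are the whole economic result. A ratio with no defined price year cannot be set beside that of another programme.

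**Working it through.** The plan states no dollar amount, cost share, inflation index or cost ratio, so there is no figure of its own to reproduce. The check sets the dates side by side and then illustrates the size under stated assumptions.

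**Step 1: the gap in years**

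| Anchor | Where | Years after 2008 |
|---|---|---|
| A cited guideline web page was consulted on 30 June 2017, so enrollment under this text came later | Section 9.0, reference 19 | 2017 − 2008 = 9 or more |
| Recruitment was held and the study period lengthened because of COVID-19 (taken as 2020) | Section 4.0, COVID-19 Response | 2020 − 2008 = 12 or more |
| Up to a further year for 63 late responders, on top of the 18 months | Section 4.0 | 2020 + 1.5 + 1 − 2008 = about 14 |

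The illustration uses 9, 12 and 14 years.

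**Step 2: which outputs use the 2008 unit costs**

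- Objective 2.1.4, part 1 (replication costs): built from materials, postage, PopSockets, personnel time and messaging (Sections 5.4 and 6.0). No Medicare unit cost enters, so it is not affected.
- Objective 2.1.4, part 2 (costs resulting from the interventions): service counts times unit costs, so it is affected.
- Both cost-effectiveness ratios: downstream plus intervention cost in the numerator, so they are affected.

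**Step 3: price factor**

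With an annual unit-price change g (assumption: 0% to 4%) and a gap of n years, f = (1 + g)^n.

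| g | n = 9 | n = 12 | n = 14 |
|---|---|---|---|
| 0% | 1.00 | 1.00 | 1.00 |
| 1% | 1.09 | 1.13 | 1.15 |
| 2% | 1.20 | 1.27 | 1.32 |
| 3% | 1.31 | 1.43 | 1.51 |
| 4% | 1.42 | 1.60 | 1.73 |

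The range is 1.00 to 1.73. Nothing in the documents excludes a fall. At −1% a year over 12 years, f = 0.99^12 = 0.89, and the 2008 schedule would overstate downstream cost.

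**Step 4: effect on a cost-effectiveness ratio**

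Let D be incremental downstream cost at 2008 prices, I the remaining incremental cost (taken as already in study-year dollars), and E the additional women screened or cancers detected.

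- Mixed-year ratio: (D + I) / E
- Common-year ratio: (fD + I) / E
- Common-year over mixed-year: 1 + s(f − 1), where s = D / (D + I)

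The documents do not give s; 50% to 95% is assumed.

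- Low end, g = 0%: 1 + s × 0 = 1.00
- Middle case, g = 2%, n = 12, s = 0.80: 1 + 0.80 × 0.268 = about 1.21
- High end, g = 4%, n = 14, s = 0.95: 1 + 0.95 × 0.732 = about 1.70

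E cancels, so the multiplier is the same for both ratios.

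**The case against.** Several points on the other side are fair.

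- **The price year is not fully explicit.** A relative value scale needs a conversion factor to become dollars, and the plan does not state that factor's year. Nor does it say that intervention costs are in study-year dollars, only that they will be collected. This stands as a limit: mixed years are the natural reading, not a written fact. It does not remove the gap, because no common year is stated under any reading.
- **Sensitivity analysis may cover the shift.** A reader might infer that the planned range is centred on the 2008 average and so must miss the right level. The text gives neither centre nor width, so that cannot be shown. Equally, it cannot be shown that the range is wide enough. Varying unit costs also does not put the components in the same year's dollars.
- **The plan commits to standard cost-effectiveness methods.** Those may include price-year alignment, but this rests on cited texts that cannot be consulted here. A general phrase does not displace a named 2008 source.
- **The economic aim is secondary.** There are no formal tests, the analysis is called limited, and services are counted before they are priced, so repricing needs no new data. All of this stands. It bounds the consequence and makes the correction easy.

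The use of Medicare rates as a proxy for resource cost is not in dispute; only the year is.

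**Conclusion.** The point holds in a bounded form. The plan ties physician and laboratory unit costs to a 2008 schedule, the services fall about 9 to 12 or more years later, and those costs are combined with trial-collected costs without a common price year or inflation step.

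On the stated assumptions the price factor is 1.00 to 1.73 and the ratios would change by a factor of 1.00 to 1.70. Neither is an estimate of bias. A reader might conclude that the 2008 schedule understates downstream cost by a definite percentage. The documents do not support that: they give no price trend, and flat or falling rates would make the distortion nil or reverse it. A reader might also take all of Objective 2.1.4 to be affected; its replication-cost part is not. The primary comparison of screening rates is untouched.

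**What to change.** In the economic part of Section 6.0:

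1. Name one reference year within the follow-up period.
2. Price all physician and laboratory services with that year's Medicare fee schedule, stating both the relative values and the conversion factor.
3. Express intervention costs and the literature-based patient time and travel costs in the same year's dollars, using a named index. Repricing services alone would leave time and travel costs in an unstated year.
4. Keep the planned low-to-high sensitivity analysis around that base case, and state its width.

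The cost is a replaced lookup table and a small amount of recoding where service codes have changed. No new participant data and no change to design, sample size or primary analysis are needed.
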